### 7.3.1.2 **Eliciting and Documenting Adverse Events**

Subjects will be asked a standard question to elicit any medically related changes in their well-being. They will also be asked if they have been hospitalized, had any accidents, used any new medications, or changed concomitant medication regimens (both prescription and --over-the-counter medications).

In addition to subject observations, AEs will be documented from any data collected on the AE page of the eCRF (e.g., laboratory values, physical examination findings, and ECG changes) or other documents that are relevant to subject safety.

### 7.3.1.3 Reporting Adverse Events

All AEs reported or observed during the study will be recorded on the AE page of the eCRF. Information to be collected includes drug treatment, type of event, time of onset, dosage, investigator-specified assessment of severity and relationship to study drug, time of resolution of the event, seriousness, any required treatment or evaluations, and outcome. Any AEs resulting from concurrent illnesses, reactions to concurrent illnesses, reactions to concurrent medications, or progression of disease states must also be reported. The Medical Dictionary of Regulatory Activities (MedDRA) will be used to code all AEs.

Any medical condition that is present at the time that the subject is screened but does not deteriorate should not be reported as an AE. However, if it deteriorates at any time during the study, it should be recorded as an AE.

Any AE that is considered serious by the investigator or which meets SAE criteria ([Section 7.3.1.1](#)) must be reported to the sponsor within 24 hours of awareness (after the investigator has confirmed the occurrence of the SAE). The investigator will assess whether there is a reasonable possibility that the study drug caused the SAE. The sponsor will be responsible for notifying the relevant regulatory authorities of any SAE. The investigator is responsible for notifying the Institutional Review Board (IRB) or Ethics Committee (EC) directly as applicable per institutional policy. The sponsor or designee will provide regulatory authorities, IRB/ECs, and the investigator with clinical safety updates/reports according to local requirements

In addition to entering the AE details in the eCRF, the study site should also complete the SAE eCRF page within 24 hours of awareness. In the event that EDC entry is not possible (e.g., eCRF system failure or access problems), the study site should complete/fax the paper SAE report form and fax the form within 24 hours of awareness and update the EDC as soon as it is available.

For this study, the following contact information will be used for SAE reporting:

Email (primary):

PPD

24 Hour Safety Hotline Fax:
PPD

Back-up email: PPD

Fax (back-up): PPD

Phone (back-up): PPD

Additional follow-up information, if required or as available, should be sent as soon as possible and placed with the original SAE information.

Pregnancy is not regarded as an AE unless there is a suspicion that the study drug may have interfered with the effectiveness of a contraceptive medication. Any pregnancy that occurs during study participation must be reported using a Pregnancy Notification Form. To ensure subject safety, each pregnancy must be reported to the sponsor within 2 weeks of learning of its occurrence. All pregnancies will be followed up to determine the outcome, including spontaneous or voluntary termination, details of birth, presence or absence of any birth defects, congenital anomalies, or maternal and/or newborn complications, even if the subject was discontinued from the study. After the expected pregnancy end date, the site will complete the Pregnancy Outcome Form. Elective terminations for medical reasons should not be reported as AEs or SAEs. Spontaneous miscarriages must be reported as an SAE. Any subject who becomes pregnant during the study must be withdrawn from the study

CCI  
[Redacted]

#### 7.3.1.4 Assessment of Severity

The severity (or intensity) of an AE refers to the extent to which it affects the subject's daily activities. Severity of AEs will be graded according to the grading scales modified from DAIDS Table for Grading the Severity of Adult and Pediatric Adverse Events ([DHHS 2017](#)).

The determination of severity not listed in the DAIDS Table for Grading the Severity of Adult and Pediatric Adverse Events (DHHS 2017) should be made by the investigator based upon medical judgment and the definitions of severity as follows:

- Grade 1 (Mild): Mild symptoms causing no or minimal interference with usual social and functional activities with no intervention indicated
- Grade 2 (Moderate): Moderate symptoms causing greater than minimal interference with usual social and functional activities with intervention indicated
- Grade 3 (Severe): Severe symptoms causing inability to perform usual social and functional activities with intervention or hospitalization indicated
- Grade 4 (Potentially life-threatening): Potentially life-threatening symptoms causing inability to perform basic self-care functions with intervention indicated to prevent permanent impairment, persistent disability, or death
- Grade 5 (Death)

Changes in the severity of an AE should be documented to allow the duration of the event at each level of intensity to be assessed. An AE characterized as intermittent does not require documentation of the onset and duration of each episode.

#### 7.3.1.5 **Assessment of Causality**

The investigator's assessment of an AE's relationship to study drug is part of the documentation process.

The investigator will assess causality (i.e., whether there is a reasonable possibility that the study drug caused the event) for all AEs and SAEs. The relationship will be classified as follows:

- Not related: There is not a reasonable possibility of relationship to study drug. The AE does not follow a reasonable temporal sequence from study drug administration, or can be reasonably explained by the subject's clinical state or other factors (e.g., disease under study, concurrent diseases, and concomitant medications).
- Related: There is a reasonable possibility of relationship to study drug. The AE follows a reasonable temporal sequence from study drug administration and cannot be

reasonably explained by the subject's clinical state or other factors (e.g., disease under study, concurrent diseases, or concomitant medications), represents a known reaction to the study drug or other drugs in its class, is consistent with the known pharmacological properties of the study drug, and/or resolves with discontinuation of the study drug (and/or recurs with re-challenge, if applicable).

### 7.3.1.6 Follow-up of Adverse Events

All AEs must be reported in detail on the appropriate page of the eCRF and followed until they are resolved, stable, or judged by the investigator to be not clinically significant.

### 7.3.2 Clinical Laboratory Testing

Clinical laboratory tests will be performed by the study sites' local laboratories. Blood and urine samples will be collected, as per the SOE (Section 3) and will be prepared using standard procedures.

A repeat measurement of clinical laboratory testing is permitted for eligibility determination. Other clinical laboratory retests may be permitted once in certain scenarios with CCI approval. Such scenarios may include laboratory processing error, results inconsistent with subject's historical values/medical history, or other extenuating circumstances such as a recent or intercurrent illness potentially affecting screening laboratory results. The clinical laboratory that will perform the tests will provide the reference ranges for all clinical laboratory parameters. Abnormal clinical laboratory values will be flagged as either high or low (or normal or abnormal) based on the reference ranges for each laboratory parameter.

The following clinical laboratory assessments will be performed at site or laboratory appointed by site:

Hematology	Complete blood count (CBC) including white blood cell (WBC) count with differential count, red blood cell (RBC) count, platelet count, hematocrit, hemoglobin, red blood cell indices
Coagulation	Prothrombin time, partial thromboplastin time, and international normalized ratio (INR)
Serum chemistry	Alanine aminotransferase (ALT), alkaline phosphatase, aspartate aminotransferase (AST), bilirubin (total and direct), blood urea nitrogen (BUN), creatinine, lipase, serum creatine kinase, bicarbonate or total carbon dioxide, sodium, potassium, chloride, glucose, total protein, albumin, phosphate, calcium, and amylase

Urinalysis	Urinalysis will be performed with microscopy at indicated. Additional urinalysis may be performed as clinically indicated. It is not required to have the results from the urinalysis performed at screening before beginning study drug dosing, unless medically necessary to establish eligibility (at investigator's discretion)
Direct viral tests	SARS-CoV-2 rapid test, rapid influenza diagnostic test
Other analyses	Female subjects: Pregnancy test ( $\beta$ -HCG; urine at screening and urine or serum after screening)

Samples for the following laboratory tests will be sent to the sponsor or a designee for analysis:

- Viral Load (as measured by RT-PCR and viral titre)
- Treatment-emergent amino acid substitutions in DENV NS5 polymerase
- DENV Serotype Testing
- NS1 Antigen
- Plasma Biomarker
- Pharmacokinetic Assessment

### 7.3.3 Vital Sign Measurements

Vital signs will be measured after the subject has been in the seated position for at least 5 minutes. A repeat measurement of vital sign measurements is permitted for eligibility determination. On Day 1, vital signs will be measured before study drug administration and before any scheduled blood collections ([Section 3](#)). Subsequent measurements of vital signs (once a day on Days 2-6) may occur anytime during the day, either in the clinic or with mobile nursing staff.

Vital signs will include systolic and diastolic blood pressure, pulse rate, respiratory rate, and body temperature.

In addition, temperature will be measured orally at least every 4 hours during the study treatment period (morning, mid day, late afternoon, evening, while the subject is awake) and will be recorded in a patient diary.

### **7.3.4 12-Lead Safety Electrocardiogram**

Triplicate 12-lead ECG recordings will be performed as listed in the SOEs ([Section 3](#)) after the subject has been in the supine position for at least 5 minutes.

Measurements of the following intervals will be reported: RR interval, PR interval, QRS width, QT interval, and Fridericia's corrected QT interval (QTcF). Assessments should include comments on whether the tracings are normal or abnormal; rhythm; presence of arrhythmia or conduction defects; morphology; any evidence of myocardial infarction; or ST-segment, T Wave, and U Wave abnormalities.

### **7.3.5 Physical Examinations**

A complete physical examination will include, at minimum, assessment of skin, head, ears, eyes, nose, throat, neck, thyroid, lungs, heart, cardiovascular, abdomen, lymph nodes, and musculoskeletal system/extremities. A symptom-targeted physical examination will be conducted based on the specific symptoms targeted. Interim physical examinations may be performed at the discretion of the investigator, if necessary, to evaluate AEs or clinical laboratory abnormalities.

## **8. STATISTICAL ANALYSIS**

Details of all statistical analyses will be described in a separate statistical analysis plan (SAP).

### **8.1 SAMPLE SIZE CALCULATIONS**

The sample size for this study is approximately 60 subjects. Each of the 3 cohorts will include 20 subjects (15 subjects receive AT-752 and 5 subjects receive placebo).

In Low et al ([Low 2014](#)), the observed standard deviations for VLR, defined as mean change from baseline viral load on days 2, 3, and 4, ranged from 0.75 (N=26) to 1.07 (N=24). Taking into account that the VLR endpoint in that study was based on an average of 3 measurements and assuming that there is some correlation between measurements on days 2 through 4, we consider power to detect a true effect at a single time point using a one-sided 0.10 level test (unadjusted for multiple comparisons) with N=15 per arm for standard deviations in a range from 1 to 1.75:

True standard deviation	Effect (log 10 copies/ml) with 80% power (N=15 vs. 15)  Comparison versus placebo pooled across 3 planned cohorts	Effect (log 10 copies/ml) with 80% power (N=15 vs. 5)  Comparison versus placebo within a cohort
1	0.8	1.1
1.25	1	1.4
1.5	1.2	1.7
1.75	1.4	2.0

Based on the above table, there is 80% power to detect a true treatment effect (versus placebo) on change-from-baseline viral load of 1 log10 at a time point if the true SD is 1.25 for comparison of groups with N=15 each. The analogous power to detect a 1 log10 effect for a within cohort comparison is 59%. Furthermore, if true SD is in the range from 1 to 1.75, the probability that the observed effect would be 0.5 log10 or larger is low (in range from 0.09 to 0.22) if there is no treatment effect, i.e., an observed effect of 0.5 or larger might be considered suggestive of a signal. Interpretation of results will consider the totality of the data.

## 8.2 ANALYSIS SETS

The analysis populations are as follows:

- The primary analysis population is the modified intent-to-treat (mITT) population, which will include all randomized subjects who received at least 1 dose of study drug and have baseline and at least 1 post-baseline virology measurement. The primary analysis will also be performed on the per-protocol population of patients who completed treatment without a major protocol deviation.

- The PK population will include subjects who receive at least 1 dose of the study drug and have sufficient concentration data to support accurate estimation of at least 1 PK parameter.
- The safety population will include all subjects who receive at least 1 dose of study drug.
- A per protocol population will include the subset of the modified intent-to-treat population who completed study drug treatment without a major protocol violation.

### **8.3 PLANNED STATISTICAL ANALYSIS**

Safety, PK, and PD data will be summarized in tabular and/or graphical format by active dose treatment arms and a-pooled placebo arm. Continuous data will be summarized using descriptive statistics (n, mean, standard deviation [SD], median, 95% confidence interval [CI]) and categorical data will be summarized using counts and percentages. All subject-level data will be presented in listings.

Baseline demographic and background variables will be summarized overall for all subjects. The number of subjects who enroll in the study and the number and percentage of subjects who complete the study will be presented. Incidence and percentage of subjects who withdraw or discontinue from the study and from treatment, and the reason for withdrawal or discontinuation, will also be summarized.

Baseline is the last measurement prior to the start of study drug.

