## **2. STUDY OBJECTIVES**

The primary objective of this study is:

- To investigate the antiviral activity of AT-752 versus placebo in terms of reduction of DENV RNA from baseline in adult subjects with confirmed DENV infection

The secondary objectives of this study include PK and safety objectives as outlined below.

The PK objective of this study is:

- To evaluate the PK of AT-752 (AT-281) and metabolites in adult subjects with confirmed DENV infection.

The safety objective of this study is:

- To evaluate safety of AT-752 versus placebo in adult subjects with confirmed DENV infection

The exploratory objectives of this study include PD objectives as outlined below:

[figure not shown]
- To describe the effect of AT-752 on viremia (viral titre), DENV nonstructural protein 1 (NS1) levels, fever, and biomarkers (see list in [Section 8.3.4](#)) compared to placebo in adult subjects with confirmed DENV infection

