### **8.3.4 Pharmacodynamic Exploratory Analyses**

- Change in DENV viral load (as measured by viral titre) from baseline
- Area under the log10-transformed viral load curve (AUC) from first dose to the end of treatment (Day 5-6) and to study end (Day 28) (as measured by DENV RNA and viral titre)

- Time to viral load (as measured by DENV RNA and viral titre) or NS1 clearance, defined as time to first of 2 consecutive undetectable viral load or NS1, will be described using Kaplan-Meier methods. The median time to viral clearance and the estimated proportions of patients with viral clearance will be summarized by treatment group. Patients who do not receive a record a negative test result by RT-PCR/viral titre or NS1 antigen assay by the last observation timepoint will be treated as censored at the final scheduled evaluation time point.
- Change of DENV viral load (as measured by DENV RNA and viral titre) from baseline, viral load AUC, time to viral load or NS1 clearance by DENV serotype
- Treatment-emergent amino acid substitutions in DENV NS5 gene
- 
- Methods for analysis of time to resolution or duration of fever will be presented in the SAP
- Exploratory biomarkers may include plasma concentrations of cytokines (for example, TNF- $\alpha$ , IFN- $\gamma$ , IL-2, IL-4, IL-5, IL-6, IL-10, IL-12, IL-13, IL-1 $\beta$ , IP-10 and MCP-1)
- Exploratory analyses may be performed to evaluate exposure-response relationship. The relationship between the exposure of AT-752 (and its metabolites) and DENV viral load may be explored using graphical displays

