## **2.3 Exploratory Objectives**

- To describe the effect of AT-752 on viremia (viral titre), DENV nonstructural protein 1 (NS1) levels, fever, and biomarkers (see list in [section 12](#)) compared to placebo in adult subjects with confirmed DENV infection

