#### 4. General Statistical Considerations

All statistical analyses will be conducted using statistical analysis system SAS® Version 9.4 or higher (SAS Institute, Cary, NC).

Analysis of the data from this study will be descriptive in nature. Confidence intervals and p-values will be descriptive due to small sample size in this study. N, mean, standard deviation, median, minimum and maximum, and 95% CI will be used for continuous data and number and percentage

will be used for categorical/count data, unless specified otherwise. No analysis will be performed until the data are unblinded.

All tables, listings, and figures will be presented by assigned treatment. The treatments below will be used for presentations:

- AT-752 750 mg TID
- AT-752 up to 1000 mg BID or TID
- AT-752 up to 1500 mg BID
- Placebo (pooled Cohort 1 through Cohort 3)

All data listings will be sorted by treatment and subject number. If a regimen is repeated in more than one cohort, the matching cohorts will be pooled as one treatment.

Unless otherwise specified, no algorithm for imputation of missing data will be employed.

Study days are calculated with respect to the first date of study drug exposure (First Dose Date) as below:

- If the assessment/observation date is on or after the first dose date, then  
Study Day = Assessment/Observation Date – First Dose Date + 1;
- Otherwise, Study Day = Assessment/Observation Date – First Dose Date

Baseline will be defined as the last non-missing assessment (including repeated and unscheduled assessments) before administration of the first dose of study drug, unless otherwise specified.

For summary of safety assessments, if there are repeated measurements at a time point, the first non-missing assessment at that time point will be used in the summary tables.

Unscheduled results will not be included in the summary tables, except for determining baseline, but will be presented in data listings.

The methodology and data handling specifications for PK data are detailed in Section 11.

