Intermediate missing log 10-transformed viral loads (between baseline and the last day) will be linearly interpolated using the last and next available viral loads for AUC calculation for both AUCD5 and AUCD28. Subjects with intermediate missing values will be included in AUC analysis.

Time to viral load (as measured by DENV RNA and viral titre) or NS1 clearance, defined as time to first of 2 consecutive results of undetectable viral load or NS1, will be described using Kaplan-Meier methods. The median time to viral clearance and the estimated proportions of patients with viral clearance will be summarized by treatment group. Patients who do not receive a record of a negative test result by RT-PCR/viral titre or NS1 antigen assay by the last observation timepoint will be treated as censored at the final scheduled evaluation time point.

Subgroup analysis by DENV serotype will be carried out for the following endpoints: change of DENV viral load (as measured by DENV RNA and viral titre) from baseline, viral load AUC, time to viral load or NS1 clearance. Descriptive statistics (N, mean, standard deviation, median, minimum and maximum, and 95% CI) will be presented by treatment group.

Number and percentage of subjects with treatment-emergent amino acid substitutions in DENV NS5 gene will be compared between the treatment groups (chi-squared test).

Duration of fever is the sum of fever episode durations where fever episode duration is defined as the time from first fever measurement (either at baseline or following a period without fever) to the next measurement without fever. If the last episode has not resolved, duration for that episode will be

censored at the time of the last temperature measurement. Treatments will be compared by log-rank test.

Exploratory biomarkers may include plasma concentrations of cytokines (for example, TNF- $\alpha$ , IFN- $\gamma$ , IL-2, IL-4, IL-5, IL-6, IL-10, IL-12, IL-13, IL-1 $\beta$ , IP-10 and MCP-1). Data will be presented in descriptive statistics by treatment.

Exploratory analyses may be performed to evaluate exposure-response relationship. The relationship between the exposure of AT-752 (AT-281 and its metabolites AT-551, AT-229, and AT-273) and DENV viral load may be explored using graphical displays. Scatter plots of drug exposure versus change in DENC viral load will be provided.

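### For cytokines the SAP specifies no log scale, no use of the pre-dose sample and no contrast with pooled placebo, although the objective is a comparison with placebo

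*Protocol*

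**What the plan says.** The exploratory objective in SAP 2.3 is "To describe the effect of AT-752 on viremia (viral titre), DENV nonstructural protein 1 (NS1) levels, fever, and biomarkers", and Protocol section 2 frames the same objective as "compared to placebo in adult subjects with confirmed DENV infection". The measures are optional: Protocol 8.3.4 says "Exploratory biomarkers may include plasma concentrations of cytokines" and names twelve as examples.

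The analysis of these cytokines is one sentence in SAP section 12: "Data will be presented in descriptive statistics by treatment". That falls back on the SAP section 4 default, "N, mean, standard deviation, median, minimum and maximum, and 95% CI will be used for continuous data and number and percentage" for categorical data. Protocol 8.3 has the parallel default for safety, PK and PD data: "Continuous data will be summarized using descriptive statistics (n, mean, standard deviation [SD], median, 95% confidence interval [CI". It does not mention cytokines. SAP section 4 also says "Confidence intervals and p-values will be descriptive due to small sample size in this study".

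On size, Protocol 8.1 states "Each of the 3 cohorts will include 20 subjects (15 subjects receive AT-752 and 5 subjects receive placebo". SAP section 4 presents one placebo group pooled over the three cohorts. The schedule of events puts plasma biomarker samples at screening and on Days 1, 2, 4, 6, 8, 14 and 28, and both documents define baseline as the last pre-dose value.

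Other measures get more. DENV RNA (SAP 8.1.1) and viral titre (SAP 12) are analysed as change from baseline with baseline viral load in the model. Plasma drug concentrations (SAP 11) get geometric means and geometric CVs.

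**The concern.** An objective worded as an effect against placebo needs some contrast with placebo, and the plan gives cytokines none. Two further features weaken what the by-arm summaries can show.

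- **Scale.** If cytokine concentrations are right-skewed, one or two high values among 15 patients drive the arithmetic mean and SD, and a t-interval labelled 95% covers less than that.
- **Baseline.** Each patient has a pre-dose sample that the plan does not use. Arms of 15 will often differ at baseline by chance. The comparator is also only partly concurrent: 10 of the 15 planned placebo patients belong to cohorts other than the one an active arm was randomised in. Either kind of difference persists after dosing and cannot be told apart from drug effect in unadjusted post-dose summaries.

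At stake is the usefulness of the biomarker results for dose selection and understanding of mechanism, not the primary conclusion.

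**Working it through.** **The plan's own figures.** No figure is stated for biomarkers. The sample size rests on viral load: a 1 log10 effect, SD 1.25, one-sided 0.10. A noncentral t calculation gives 81.0% power for 15 vs 15 and 59.2% for 15 vs 5, against the stated 80% and 59%. These reproduce and are not in question.

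**Inputs.** From the documents: 15 patients per active arm and 3 × 5 = 15 pooled placebo. Assumed, because the documents give neither: log-normal concentrations with log-SD s from 0.5 to 1.5, and a correlation r between log baseline and log post-dose value of 0.3 to 0.8.

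**Step 1: interval for one arm.** In 400,000 simulated samples of n = 15, take the interval mean ± t(0.975, 14 df) × SD/√15 and count how often it contains the true mean exp(s²/2). CV = √(exp(s²) − 1).

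| log-SD | CV | Coverage | True mean above upper limit | True mean below lower limit | Lower limit < 0 |
|---|---|---|---|---|---|
| 0.5 | 53% | 92.6% | 6.7% | 0.7% | 0.0% |
| 0.75 | 87% | 89.8% | 9.9% | 0.3% | 0.2% |
| 1.0 | 131% | 85.6% | 14.3% | 0.1% | 3.0% |
| 1.5 | 291% | 74.3% | 25.7% | 0.02% | 24.6% |

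Nearly all misses are on one side, so the interval is misplaced as well as short. The log-scale interval covers 95.0% in every row. That follows from assuming log-normality, and it refers to the geometric mean, a different quantity.

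**Step 2: does this create false arm differences?** Simulate two arms of 15 with the same distribution. The 95% Welch interval for the difference covers 95.6% to 97.9% over s = 0.5 to 1.5, and two per-arm 95% intervals fail to overlap in only about 0.4% to 0.6% of pairs. So it does not.

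**Step 3: chance baseline gaps (log scale, units of the log-SD).** The SE of a baseline difference is √(2/15) = 0.365. The probability of a gap above 0.5 is 2 × [1 − Φ(0.5/0.365)] = 17%. Such a gap carries an expected 0.5 × r into post-dose values: 0.25 at r = 0.5 and 0.40 at r = 0.8.

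**Step 4: gain from using baseline (15 vs 15).**

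- Post-dose values only: √(2/15) = 0.365.
- Change from baseline: √(2(1 − r) × 2/15) = 0.432, 0.365 and 0.231 at r = 0.3, 0.5 and 0.8.
- Baseline as covariate: √((1 − r²) × 2/15) = 0.348, 0.316 and 0.219 at the same r.

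The covariate reduces the SE by 1 − √(1 − r²): 13% at r = 0.5 and 40% at r = 0.8. That is the precision of 15/0.75 = 20 or 15/0.36 ≈ 42 patients per arm. Simple change helps only if r exceeds 0.5. The covariate costs one degree of freedom, which the formula ignores.

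**The case against.** The case for leaving the plan alone is reasonable. The biomarkers are optional and exploratory, and the objective is to describe. By-arm summaries that include placebo are a description. Intervals are labelled descriptive, and no cytokine test is planned. Median, minimum, maximum and subject listings would expose extreme values, and a by-visit table could show a baseline imbalance. All of this stands, and it keeps the point minor.

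Several stronger readings are tempting and should be resisted.

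- **That the plan prescribes raw means.** It is silent on scale. The raw scale is only the natural reading of the default.
- **That the intervals are known to be too narrow.** The documents give no SD, CV or skew for cytokines. At log-SD 0.5 the shortfall is about two points.
- **That baseline differences will pass for drug effect.** No contrast is tested. Under concurrent randomisation, unadjusted values add noise rather than systematic bias, and step 2 shows no excess of false differences. Step 2 does assume the same distribution in every cohort. Randomisation does not protect the non-concurrent placebo patients, but the documents give no evidence of drift between cohorts.

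The fuller analysis also has a price. Twelve cytokines × six post-baseline visits × three doses is 216 ratios; if all true ratios were 1, about 0.05 × 216 ≈ 11 of the 95% intervals would exclude 1.

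**Conclusion.** The point holds as a cheap improvement to an exploratory analysis. The objective is a comparison with placebo, and for cytokines the SAP specifies no placebo contrast, no use of the pre-dose sample and no log scale, while it handles viral load and drug concentrations with more care.

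The two sizes rest on separate assumptions. Coverage of the arm-mean interval falls to about 93%, 86% and 74% at log-SD 0.5, 1.0 and 1.5 if concentrations are log-normal. The 13% to 40% reduction in the SE of an arm difference needs a baseline correlation of 0.5 to 0.8; at 0.3 it is only about 5% (0.365 to 0.348). Undercoverage and chance baseline gaps cost precision and clarity; they do not inflate false differences between equal arms. Baseline adjustment would also remove the part of any between-cohort difference that already shows before dosing. Nothing here touches the primary endpoint, the safety analysis or the sample size.

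**What to change.** Amend the cytokine paragraph in SAP section 12:

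1. Analyse each cytokine as log10 concentration.
2. By visit and arm, report the geometric mean ratio to baseline with a 95% CI.
3. By visit, report the ratio of each dose to pooled placebo with a 95% CI, from a model with log baseline as covariate. Label these descriptive and unadjusted for multiplicity.
4. State one cytokine rule for values below the LLOQ, for example 0.5 × LLOQ, and show the number of such values by arm and visit. Do not borrow the viral-load rule by reference: SAP 8.1.1 and section 10 use 0.5 × LLOQ, while SAP 8.1.2 counts such values as 0 in log10 summaries. If many values fall below the LLOQ, the log-scale interval will not keep its nominal coverage either.
5. Keep the median, minimum and maximum.

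The cost is a few sentences and some table shells, with no new data. The downsides are results stated as ratios and many unadjusted exploratory intervals.
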